9.1 Serious Adverse Events Reporting	
9.2 Planned Interim Safety Analysis	
9.3 Planned Stopping Rules	
9.4 Planned Rules for Participant Withdrawal	
10 REFERENCES	17

PROJECT TITLE

Routine Preoperative Molecular Analysis to Guide Extent of Surgery in Thyroid Cancer, a Pilot Feasibility Study

SUMMARY

Ideal surgical extent for differentiated thyroid cancer remains unclear. Routine use of molecular analysis in biopsy-proven thyroid cancer could provide important prognostic information to help guide extent of surgery – thyroid lobectomy versus total thyroidectomy. This is a pilot feasibility study for the use of routine molecular analysis in Bethesda V and VI thyroid cancers, with randomization of the intermediate-molecular risk subgroup to thyroid lobectomy and total thyroidectomy. We hypothesize that patients will 1) agree to preoperative molecular analysis, and 2) 50% of intermediate-risk patients will agree to and follow through with randomization. This will be a pilot study for a future randomized controlled trial (RTC) to compare between the two surgical approaches in intermediate-molecular risk thyroid cancer.

BRIEF DESCRIPTION OF STUDY KEY WORDS

RAI Radioactive iodine
PTC Papillary thyroid cancer

NIFTP Non-invasive follicular thyroid neoplasm with papillary-like nuclear features

ATA American Thyroid Association

FNA Fine needle aspiration PTH Parathyroid hormone

TSH Thyroid stimulating hormone

Tg Thyroglobulin

EMR Electronic Medical Record

2. ABSTRACT

Every year, ~45,000 individuals in the United States develop a new diagnosis of thyroid cancer. Initial therapy for most patients involves surgical excision of the thyroid lobe containing the cancer (thyroid lobectomy) or removal of the entire gland (total thyroidectomy). Compared to thyroid lobectomy, total thyroidectomy carries double the risk of recurrent laryngeal nerve injury, adds the possibility of permanent hypoparathyroidism, and makes all patients dependent on lifelong thyroid hormone supplementation. We accept these additional risks because total thyroidectomy allows patients to receive postoperative radioactive iodine (RAI) therapy, which mitigates recurrence risk in high-risk patients. Thus, total thyroidectomy primarily benefits patients that require radioiodine remnant ablation. Unfortunately, the need for RAI ablation relies on postoperative pathology findings and cannot be reliably predicted preoperatively. The current problem is that some patients in this system receive overly aggressive care, undergoing the additional risk of total thyroidectomy but ultimately not requiring radioactive iodine. Others may receive overly conservative initial treatment, needing reoperation for a completion thyroidectomy after initial thyroid lobectomy. Thus, there is a clear, unmet need for preoperative prognostic risk stratification to determine ideal surgical treatment for thyroid cancer.

One potential solution is to risk-stratify thyroid cancer patients based on molecular testing. Currently, molecular analysis is used to differentiate benign nodules from potentially cancerous nodules but it is not utilized for prognostic purposes. Several studies have determined that high-risk mutation profiles, such as *TERT* and *TP53*, ^{1,2} predict metastatic and recurrent disease. As such, if mutation status was known preoperatively, these patients could be directed to undergo a total thyroidectomy. Conversely, lower risk lesions could be directed to thyroid lobectomy. There would still be a large area of uncertainty among intermediate molecular-risk lesions, such as isolated *BRAF*, ³ for which there are no recommendations on extent of treatment.

To date, no randomized control trial exists comparing extent of surgery based on preoperative molecular data. We envision a future clinical trial where thyroid cancer patients undergo risk stratification with molecular testing, and subsequently intermediate-molecular risk patients get randomized to thyroid lobectomy versus total thyroidectomy. To determine how to adequately power this endeavor, we propose a pilot randomized clinical trial as an initial feasibility study. We hypothesize that 1) patients with papillary thyroid cancer will agree to preoperative molecular testing, and 2) 50% of intermediate molecular-risk patients will agree to randomization to thyroid lobectomy versus total thyroidectomy and complete treatment as assigned.

Patients referred to our Endocrine Surgery Clinic with new diagnosis of papillary thyroid cancer (Bethesda V or VI on cytology) will be enrolled and undergo routine molecular testing. We will exclude patients with hard indications for total thyroidectomy on ultrasound imaging (nodal or distant metastases, extrathyroidal extension). Patients' thyroid cancer molecular profile will be classified as low, intermediate, or high molecular-risk based on previous published data. There is equipoise between thyroid lobectomy and total thyroidectomy for intermediate risk molecular profile thyroid cancers. Thus, we will randomize those patients to thyroid lobectomy or total thyroidectomy. Endpoints are related to feasibility of a future trial. We will assess percentage of patients who 1) agree to randomization, and 2) complete treatment as assigned.

We will simultaneously create a registry tracking the final surgical pathology and clinical results of low and high molecular-risk patients. Postoperative pathologic findings following thyroid surgery will be obtained using chart review. We will determine whether certain mutations and molecular risk profiles predict the need for RAI treatment. Additionally, we will track postoperative cancer surveillance outcomes, including biochemical and structural evidence of recurrence.

3. STUDY RATIONALE

Incidence of thyroid cancer has substantially increased in the past decade.4 Papillary thyroid cancers (PTC), typically follow a very indolent course. Although approximately 45,000 patients are diagnosed with thyroid cancer each year, only 2,000 patients die from it with a 5-year survival of over 98%.⁴ Thus, there has been a movement to de-escalate care to reduce unnecessary surgical morbidity, and current guidelines recommend consideration of thyroid lobectomy over total thyroidectomy when appropriate.⁵ At this time, it is unclear when thyroid lobectomy would be more beneficial than total thyroidectomy. A systematic review of guidelines and expert consensuses from 2009 to 2019 for PTC 1-4 cm in size found that 11 studies recommended total thyroidectomy, recommended thyroid lobectomy, and recommended patient-centered decision making.⁶ Improved preoperative risk stratification can play a significant role in determining ideal surgical treatment of thyroid cancer.

Currently, molecular testing is used to determine the risk of malignancy in indeterminate thyroid biopsies. However, these tests have not been used for prognostic purposes in biopsy-proven thyroid cancer. Recent studies have demonstrated that the molecular profile of thyroid cancer is predictive of recurrent disease.^{2,7} Certain high-risk mutation combinations such as BRAFV600E and TERT are associated with increased risk of recurrence and fatal disease.^{1,7} Therefore, molecular testing can offer valuable prognostic information to guide treatment.

[figure not shown]
This proposal is intended to be a feasibility study to assess whether patients will agree to routine preoperative molecular testing and whether patients would complete assigned treatment following randomization. The results of this pilot randomized control trial will inform the design of a future multicenter trial. Demonstrating that molecular profile can be used to dictate initial therapy for thyroid cancer will have an immediate and dramatic impact on the field. It can accomplish our goal of reducing overtreatment and its associated morbidity in the treatment of thyroid cancer.

4. BACKGROUND

Diagnosis of thyroid cancer. Patients with thyroid nodules that look concerning for malignancy on ultrasound undergo fine needle aspiration biopsy. The cytology is classified into the Bethesda Category based on risk of malignancy. Bethesda I is non-diagnostic and repeat biopsy is required, and Bethesda II is benign. Bethesda III and IV are indeterminate nodules with a 5-30% risk of malignancy. Bethesda V and VI have an 85-100% risk of malignancy, so those patients require operative resection. Molecular testing was first employed in Bethesda III and IV lesions to better delineate the risk of malignancy. However, we have not yet used these molecular tests on Bethesda V or VI lesions for prognostic purposes.

Thyroseq molecular analysis. As mentioned above, patients with indeterminate thyroid nodules undergo molecular analysis of the biopsy sample to determine risk of malignancy based upon mutations and gene alterations that are present. In this proposal, we plan to utilize Thyroseq for the analysis, which is a DNA-and RNA-based next generation sequencing model of 112 genes.⁸ Molecular analysis models were trained with machine learning algorithm on both pathologies that were confirmed to be benign (Bethesda II) and malignant (Bethesda V and VI) to analyze which genes and mutations are associated with malignancy.⁹ It reports the analysis in six different categories that range from negative to presence of high-risk mutation (Figure 1). Based on Thyroseq's risk stratification, nodules with certain combinations of TERT/TP53 with BRAF mutations are considered high risk for recurrence,² and total thyroidectomy is recommended. Conversely, RAS-like mutations are associated with non-invasive follicular thyroid neoplasm with

papillary-like nuclear features (NIFTP), or a very low-risk variant of papillary thyroid cancer.¹⁰ Thus, a thyroid lobectomy is recommended for these low-risk cases. However, there exists a gray area in the appropriate management of intermediate-molecular risk mutations, such as Hurthle cell-type mutation and BRAF-type mutation, where thyroid lobectomy or total thyroidectomy are both considered adequate

treatments.

Thyroidectomy for thyroid cancer. Most patients can either undergo thyroid lobectomy or total thyroidectomy as initial surgical treatment of their thyroid cancer. For patients with disease involving the lymph nodes or soft tissues of the neck, total thyroidectomy is indicated so that patients can receive postoperative treatment with RAI. Thus, it is important for patients with diagnosed thyroid cancer to undergo ultrasound of the neck to assess for sonographic evidence of extrathyroidal spread and lymph node metastasis.5 For cancers < 1 cm limited to the thyroid, thyroid lobectomy is sufficient because those patients do not benefit from RAI. However, those who fall in the middle with nodules between 1 cm and 4 cm without evidence of disease spread, which accounts for most thyroid cancer patients, the ideal extent of surgery is uncertain and frequently debated. Since total thyroidectomy has a higher risk of recurrent laryngeal nerve injury and hypoparathyroidism, and renders all patients hypothyroid, it should be avoided if there is no clinical benefit.

Postoperative RAI for high-risk disease on pathology. Patients who ultimately end up with high-risk disease on pathology (extrathyroidal extension, numerous lymph node involvement, high-risk histologic features, etc.) undergo RAI therapy. In order to receive RAI, patients must have a total thyroidectomy. Those who initially had thyroid lobectomy and pathology returns with high-risk disease undergo reoperation for completion thyroidectomy – removal of the remaining thyroid gland – prior to starting RAI. The response to therapy is then assessed based on thyroglobulin levels, which are proteins secreted by thyroid tissues. Complete response would mean patients have undetectable serum thyroglobulin levels. As such, patients can be monitored for disease recurrence by serially checking thyroglobulin levels.

Molecular analysis and associated with aggressive disease. Commercially available molecular testing was first developed to discriminate benign from malignant thyroid nodules when cytology was indeterminate. Over time, there has been a growing understanding that certain molecular profiles are associated with worse clinical outcomes. Yip et al. verified a method of risk stratification of thyroid cancers based on their molecular profile by performing a propensity-matched retrospective molecular analysis of 62 differentiated thyroid cancers with distant metastases to those without distant metastases.¹¹ They found that high-

molecular risk profiling had a strong association with distant metastases (odds ratio 25.1, 95% confidence interval [CI] 3.07 – 204.4) and no patients with low-molecular risk had metastatic disease. In this instance, molecular profile predicted clinical behavior, which led us to hypothesize that molecular risk could be used to dictate therapy in thyroid cancer. This molecular risk stratification is utilized by Thyroseq (Figure 1).

Most recently, our group published a retrospective study of molecular profiles of 100 Bethesda V and VI thyroid nodules and assessed their associated risk of recurrence. Majority of the nodules in this population harbored an intermediate molecular-risk profile (6 low-risk, 88 intermediate-risk, and 6 high-risk). ¹² Similar to the study by Yip et al., high-molecular risk patients had higher rates of recurrence at 67% compared to intermediate-risk at 7%, and no recurrence in the low-risk cohort. High-risk molecular profile was associated with risk of disease recurrence in the 5-year follow-up period (hazard ratio 1.36, 95% CI 1.02 – 1.80). Based upon this data, it appears that total thyroidectomy can be reserved for high-risk individuals and thyroid lobectomy in low-risk patients. However, the ideal extent of initial surgery in intermediate-risk disease remains unclear.

5. STUDY OBJECTIVE

[figure not shown]
Aim 1. Determine feasibility of a future multi-center prospective trial of routine preoperative molecular testing for papillary thyroid cancers to guide extent of therapy. Patients with a new diagnosis of papillary thyroid cancer will undergo routine molecular testing with Thyroseq genomic classifier. Inclusion criteria include age over 18 years and cytology consistent with papillary thyroid cancer. We will exclude patients with hard indications for total thyroidectomy on ultrasound imaging (nodal or distant metastases, extrathyroidal extension). Patients' thyroid cancer molecular profile will be classified as low-, intermediate-, or high-risk based on previous published data. 11,12 Endpoints are related to feasibility of a future trial, including enrollment rate among eligible patients and drop-out rate among enrolled patients.

Aim 2. Determine the percent of eligible patients that undergo randomization to thyroid lobectomy versus total thyroidectomy and complete assigned treatment. There is equipoise between thyroid lobectomy and total thyroidectomy for intermediate risk molecular profile thyroid cancers. Thus, we will randomize those patients to thyroid lobectomy or total thyroidectomy. However, many patients may object to randomization or may not be willing to undergo treatment as randomized. Thus, we will assess percentage of patients who 1) agree to randomization, and 2) complete treatment as assigned.

Aim 3. Determine whether preoperative molecular testing predicts postoperative clinicopathologic findings by creating a registry tracking the final surgical pathology and clinical results.

6. SCHEMA

MAPS: Molecular Analysis for Precision Surgery in Thyroid Cancer, a Pilot Study

7. METHODS

7.1 STUDY DESIGN

Prospective, randomized pilot feasibility study

7.2 CRITERIA FOR SUBJECT ELIGIBILITY

Population

Adult patients with biopsy-proven papillary thyroid cancer presenting to UCLA Endocrine Surgery Clinic for surgical consultation

7.2.1 Inclusion Criteria:

- Patients aged 18 years or older at the time of enrollment,
- Biopsy proven differentiated thyroid cancer measuring 1cm to 4cm in diameter, defined as:
 - o Bethesda V or VI thyroid nodule, OR
 - o Bethesda III or IV thyroid nodule with molecular analysis showing mutation consistent with malignancy
- Molecular analysis result with intermediate molecular risk mutation:
 - o Isolated BRAF V600E
 - Isolated *BRAF*-like gene alteration
 - NTRK3 fusion
 - RET fusion
 - BRAF fusion
 - o Copy number alteration of genome haploidization type

7.2.2 Exclusion Criteria:

- Prior thyroid operation
- Extrathyroidal extension or lymph node metastases seen on ultrasound
- Distant metastatic disease

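### Section 7.2.1 admits Bethesda III/IV nodules that already have a molecular result, and Section 7.5 pools them with Bethesda V/VI in one enrolment rate, so that rate does not answer whether Bethesda V/VI patients will accept routine testing

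*Combined protocol and SAP*

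**What the plan says.** All references are to the combined protocol and SAP.

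- **Summary.** "This is a pilot feasibility study for the use of routine molecular analysis in Bethesda V and VI thyroid cancers". Its first hypothesis is that patients will agree to testing before surgery.
- **Section 2 (Abstract).** Patients with a "new diagnosis of papillary thyroid cancer (Bethesda V or VI on cytology) will be enrolled and undergo routine molecular testing".
- **Section 5, Aim 1.** "Inclusion criteria include age over 18 years and cytology consistent with papillary thyroid cancer". No Bethesda category is named. The endpoint is enrolment among eligible patients.
- **Section 7.2.1.** Cancer is defined by two routes: "Bethesda V or VI thyroid nodule, OR" a "Bethesda III or IV thyroid nodule with molecular analysis showing mutation consistent with malignancy". A separate criterion, applying to both routes, is a "Molecular analysis result with intermediate molecular risk mutation".
- **Section 3.** "Currently, molecular testing is used to determine the risk of malignancy in indeterminate thyroid biopsies". Section 4 likewise says that testing began in Bethesda III/IV, calls those categories indeterminate, and says the tests have not yet been used for prognosis in V/VI.
- **Section 4, planning data.** The group's own "retrospective study of molecular profiles of 100 Bethesda V and VI thyroid nodules" found 6 low-, 88 intermediate- and 6 high-risk.
- **Section 7.5.** The enrolment rate is patients enrolled over patients screened. It is not split by Bethesda route, neither term is defined, and no test-acceptance rate is listed.
- **Section 7.2.3.** Interested patients whose molecular result is pending are enrolled, and withdrawn later if the result makes them ineligible.

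**The concern.** The pilot's new step is offering a molecular test to patients whose cytology already points to cancer. Whether they accept it is hypothesis 1. A Bethesda III/IV patient qualifies under Section 7.2.1 through a test that the protocol describes as current practice, so the study's offer of testing is not what produced the result. Counting such a patient as enrolled gives no information on hypothesis 1.

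The populations also differ between sections. The Summary and Abstract name Bethesda V/VI. Aim 1 asks for cytology in keeping with papillary cancer, which indeterminate III/IV cytology does not meet. Section 7.2.1 is wider than all three.

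At stake is the figure handed to the multicentre trial. A pooled rate moves with the proportion of III/IV patients who happen to attend this clinic, so another centre with a different mix could not use it to forecast uptake of testing in Bethesda V/VI.

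**Working it through.** **The plan's own figure.** Section 7.2.5 expects 50% of intermediate-risk patients to agree and complete treatment as assigned, and wants 50 in the randomization cohort: 50 / 0.5 = 100. This reproduces the stated target, and nothing below changes it. For scale, at 88% intermediate, 100 / 0.88 = 113.6, so about 114 Bethesda V/VI patients must be tested to find 100.

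**Inputs from the documents.** Intermediate share in V/VI: 88/100 (exact 95% CI 80.0% to 93.6%). Agreement: q = 0.5, borrowed from Section 7.2.5 as a stand-in for consent and applied to both routes.

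**Inputs the documents do not give (assumed, shown as ranges).** Test acceptance in V/VI: a = 0.6, 0.8, 1.0. Share of III/IV among those screened: s = 0.2 (0.1 and 0.3 also shown). Share of mutation-positive III/IV nodules that are intermediate-risk: f = 0.3 to 0.88.

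**Formula.** Pooled rate = (1 − s) × V/VI rate + s × III/IV rate. The result depends on what is counted as screened and enrolled, which the plan leaves open.

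- **Rule A:** III/IV patients enter the denominator only once known to be intermediate. V/VI rate = a × 0.88 × q; III/IV rate = q.
- **Rule B:** every mutation-positive III/IV patient is screened. V/VI rate as in A; III/IV rate = f × q.
- **Rule C:** V/VI patients count as enrolled while the result is pending. V/VI rate = a × q; III/IV rate = q.
- **Rule D:** the denominator is eligible patients (Aim 1), so everyone has an intermediate result. Both rates = q.

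Results at s = 0.2:

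| Rule | Assumption | V/VI only | Pooled |
|---|---|---|---|
| A | a = 0.6 | 26.4% | 31.1% |
| A | a = 0.8 | 35.2% | 38.2% |
| A | a = 1.0 | 44.0% | 45.2% |
| B | a = 0.8, f = 0.3 | 35.2% | 31.2% |
| B | a = 0.8, f = 0.7 | 35.2% | 35.2% |
| B | a = 0.8, f = 0.88 | 35.2% | 37.0% |
| C | a = 0.6 | 30% | 34% |
| C | a = 0.8 | 40% | 42% |
| C | a = 1.0 | 50% | 50% |
| D | any a | 50% | 50% |

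Worked lines at a = 0.8: the V/VI rate is 0.8 × 0.88 × 0.5 = 0.352. Rule A: 0.8 × 0.352 + 0.2 × 0.5 = 0.382. Rule B with f = 0.3: 0.8 × 0.352 + 0.2 × 0.3 × 0.5 = 0.312. Under Rule A with s = 0.1 or 0.3, the pooled rate is 36.7% or 39.6%.

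**Break-even.** Under Rule B, pooling raises the rate only if f × q exceeds a × 0.88 × q, that is, if f > 0.88a. At a = 0.8 this is f > 0.704.

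**Reading.** Pooling can raise the rate, lower it or leave it unchanged. Under Rule D the mechanism disappears, but that rate then does not measure test acceptance on either route.

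**The case against.** The strongest reply is that no inflation has been shown, and that reply stands. A reader might infer several stronger points that the documents do not support.

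- **That the pooled rate is inflated.** The III/IV share and test acceptance are not given, and screened is not defined. Patients with pending results may already count as enrolled, so a later low- or high-risk result need not lower the V/VI rate. Upward bias is plausible under Rule A, but Rule B can reverse it.
- **That III/IV patients always reach the randomization offer.** The III/IV criterion asks for a malignant-type mutation; intermediate risk is a separate criterion. Section 4 places RAS-like changes at low risk and certain TERT/TP53 combinations with BRAF at high risk, so a mutation-positive III/IV patient can still fail. Conditioning only that route on a qualifying result would itself create the gap.
- **That these patients are not biopsy proven because Section 4 gives III/IV a 5-30% malignancy risk.** That figure describes III/IV nodules overall, not those with a malignant-type mutation, and Section 7.2.1 sets out its own definition.
- **That Aim 1 is restricted to Bethesda V/VI by name.** It is not; the mismatch is with its cytology wording.
- **That the sample size is wrong.** Section 7.2.5 starts from intermediate-risk patients and does not use the 88%.

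None of this makes the pooled rate informative about hypothesis 1.

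**Conclusion.** The point holds as one of population and denominator. Section 7.2.1 is wider than the population in the Summary, Abstract, Aim 1 and the in-house cohort. Section 7.5 then pools patients who were exposed to the study's new step with patients who came through existing practice. The resulting rate depends on case mix and may be biased for the Bethesda V/VI question.

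The size cannot be derived from the documents. In the illustrations at a 20% III/IV share, the pooled rate differs from the V/VI rate by between −4.0 percentage points (35.2% to 31.2%) and +4.7 (26.4% to 31.1%). Those figures rest on assumed test acceptance, III/IV share and intermediate share, on equal 50% consent in both routes, and on the counting rule chosen. They show that direction and size are open; they do not estimate the bias.

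The 88% share and the volume of about 200 patients a year should not be carried over to III/IV nodules without support: the first comes from V/VI only, and the second gives no Bethesda mix. This is a modest but worthwhile correction, because the rates are the pilot's main product.

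**What to change.** 1. **Section 7.5:** compute the Aim 1 enrolment rate in Bethesda V/VI patients. Add a test-acceptance rate in the same patients: those who agree to testing over those offered it.
2. **Section 7.5:** define screened and enrolled, and count them at the same step for both routes. State how patients enrolled with a pending result and later withdrawn are counted, and whether the denominator is screened patients (Section 7.5) or eligible patients (Aim 1).
3. **Section 7.5:** report the III/IV route as a separate row that counts toward the randomization cohort (Aim 2) only.
4. **Summary, Abstract and Aim 1:** align the population wording with Section 7.2.1, saying that III/IV patients enter for the randomization aim.

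The cost is wording, one extra row per rate and a somewhat smaller Aim 1 denominator. Bethesda category is already a data item in Section 7.4.1; the screening log would need to hold it, with the test offer and response, for patients who do not enrol. No eligible patient is lost, and the targets of 100 and 50 are unchanged.

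### Section 7.2.1 and the withdrawal rule keep only intermediate-risk patients, which conflicts with Aim 1 and the low/high-risk registry, leaves the risk-category endpoint with a one-level predictor, and leaves acceptance of testing uncounted

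*Combined protocol and SAP*

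**What the plan says.** **Restrictive text.** Section 7.2.1, the only full eligibility list in the text reviewed, requires a "Molecular analysis result with intermediate molecular risk mutation". Section 7.2.3 (enrolment and consent paragraphs) lets interested patients be enrolled while the result is awaited. It withdraws them if the result makes them ineligible and holds the consent call only if they are eligible. The only waiver it mentions covers screening of medical records.

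**Text that presupposes all risk categories.**
- Aim 1 (section 5): "Inclusion criteria include age over 18 years and cytology consistent with papillary thyroid cancer". The "molecular profile will be classified as low-, intermediate-, or high-risk based on previous published data".
- Abstract (section 2): new papillary cancer patients "will be enrolled and undergo routine molecular testing". Also: "We will simultaneously create a registry tracking the final surgical pathology and clinical results of low and high molecular-risk patients".
- Aim 3 (section 5): "Determine whether preoperative molecular testing predicts postoperative clinicopathologic findings by creating a registry tracking the final surgical pathology and clinical results".
- Section 8.2 describes benefits to low- and high-risk patients. The stopping rule in 9.3 refers to recurrence in a group that includes low-risk patients.

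**Outcomes.** The first hypothesis in the abstract is that "patients with papillary thyroid cancer will agree to preoperative molecular testing". Aim 1 names "enrollment rate among eligible patients and drop-out rate among enrolled patients". Section 7.5 lists enrolled over screened, drop-out over randomised, and completion surgery over the lobectomy arm. Its secondary endpoints include whether molecular-risk category predicts ATA risk category.

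**The concern.** The two sets of statements describe different study populations and cannot both be followed. If section 7 governs, every retained patient is in the same molecular-risk category. A predictor with one level cannot be related to anything, so one secondary endpoint yields no estimate. Aim 3 shrinks to a comparison of mutation types within intermediate risk.

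The pilot is also meant to inform a trial of routine preoperative testing. Willingness to be tested is one of its two hypotheses and an input to that trial, yet no listed ratio measures it. Finally, the enrolment rate is a listed primary feasibility outcome, and its numerator depends on a word that the plan uses for patients who have neither a result nor a signed consent.

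**Working it through.** **1. The plan's own figure.** Section 7.2.5 wants 50 in the randomisation cohort with 50% agreeing and completing: 50 / 0.5 = 100 intermediate-risk patients. This reproduces and is not in dispute. The same section gives 100 as the total enrolment. The two agree only if every enrolled patient is intermediate-risk, as in 7.2.1.

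**2. The predictor.** Under 7.2.1 plus withdrawal, the retained sample is 100 intermediate, 0 low, 0 high. The variance of the three-level category is 0, so its association with ATA category is not estimable. Specific mutations still vary, but that is not the endpoint as worded.

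**3. Patients affected.** Assumption: the 6 low / 88 intermediate / 6 high mix of the group's Bethesda V/VI series (section 4) applies. No mix is given for Bethesda III/IV entrants.
- Exact 95% interval for 88/100: 80.0% to 93.6%.
- Tested patients needed: 100 / 0.88 = 113.6, about 114. Over the interval, 100 / 0.9364 = 106.8 and 100 / 0.7998 = 125.04, so 107 to 126 rounded up.
- Non-intermediate: 113.6 − 100 = 13.6, about 14 (6.8 to 25.0).
- Low and high each: 113.6 × 0.06 = 6.8, about 7.

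Keeping these patients makes the endpoint estimable but supports description only. With 7 in a group, 0/7 has an exact 95% interval of 0 to 41%.

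**4. Acceptance of testing.** Enrolled/screened mixes three losses: refusal of testing, a non-intermediate result, and refusal of the trial. The other two outcomes in 7.5 start after randomisation. Aim 1's enrolment rate among eligible patients would approximate uptake of testing under Aim 1's own criteria, with enrolment before testing as in the abstract. Under 7.2.1, eligibility already requires a result, so the rate is conditional on having been tested.

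Precision of a tested/offered ratio at an assumed 80% acceptance:
- Best case, all 114 first tested in the study: 114/142 = 80%, exact 95% interval 73 to 86%.
- If half were tested before entry (assumption): 57/71 = 80%, interval 69 to 89%.

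The second case matters because 7.2.1 also admits Bethesda III/IV patients, who enter with a molecular result.

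**5. Meaning of *enrolled*.** Assume 200 screened. (The 200 in 7.2.5 is eligible patients per year, so this is an assumption.) Assume also that all tested patients are enrolled while pending.
- Withdrawn patients counted: 113.6 / 200 = 57%.
- Withdrawn patients not counted: 100 / 200 = 50%.
- Patients who never sign consent also left out, assuming only 50 sign: 50 / 200 = 25%.

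The gap between the first two is smaller if some patients enter with a known result.

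**The case against.** The strongest reply is that the registry is a separate activity. The abstract says that it runs alongside the trial and that pathology comes from chart review, so withdrawal in 7.2.3 could mean withdrawal from the randomised part only. Low- and high-risk patients would then supply the comparison and the predictor would vary. The text reviewed does not exclude this. It does not confirm it either: it shows no eligibility or consent route into the registry, and the withdrawal sentences carry no such limit.

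A reader might go further and infer that the study has no registry route at all. The documents do not support that. Some text after Target Enrollment, the schema, sections 7.3.3 and 7.3.4, the consent form (attachment A) and the data collection form (attachment C) were not available for this review and may describe one. Their absence here is not a fault of the plan. Even so, the withdrawal sentences would have to be reconciled with whatever they say.

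It is also fair that the loss is modest: about 7 low- and 7 high-risk patients, in a study that section 7.5 calls under-powered for oncologic outcomes. That stands and limits the weight of the registry part. It does not answer the missing count of acceptance or the undefined numerator, neither of which depends on the registry.

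**Conclusion.** The conflict is real in the current text and should be fixed. If section 7 is followed, the risk-category endpoint cannot be estimated, acceptance of testing has no outcome of its own, and the enrolment rate depends on an undefined term (57%, 50% or 25% in the illustrations above). About 14 patients (7 to 25) would be withdrawn. These sizes rest on the 6/88/6 mix, 200 screened and 50 signing, all assumptions.

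A reader might infer that the pilot as a whole is undermined. It is not: Aim 2, the drop-out and escalation outcomes and the need for 100 intermediate-risk patients are untouched, and the enrolment rate can be computed once its numerator is defined. Confidence is high for the conflict in wording and lower for whether a registry route exists elsewhere.

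**What to change.** **If the registry is intended:**
1. Make the intermediate-risk result a criterion for randomisation (7.3.5), not for entry to the study or registry (7.2.1). Take registry consent before, or independently of, the result. In 7.2.3, replace withdrawal of consenting low- and high-risk patients with: *not randomised; kept in the registry by chart review*.
2. Define *enrolled* once. State whether it includes patients later found non-intermediate and patients who never sign consent. Use that definition in Aim 1, 7.2.3, 7.2.5 and 7.5.
3. Add to 7.5: number accepting molecular testing / number of Bethesda V–VI patients offered it, leaving out those tested before entry.
4. In 7.2.5, replace the total of 100 with: *100 intermediate-risk patients, expected from about 114 tested (107 to 126) if the 6/88/6 mix applies, with about 7 low- and 7 high-risk*. Keep 50 randomised. Report cross-category results descriptively with exact intervals.

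**If the registry is no longer intended:** limit Aim 3 and the secondary endpoint to mutation types within intermediate risk. Correct the abstract, section 5 and 8.2. In 9.3, only reconcile the population named with the one studied. Keep the total of 100. Items 2 and 3 still apply.

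**Cost.** The first route needs a protocol amendment, a consent amendment if the consent form does not already cover the registry, one extra count, and chart abstraction for about 14 (7 to 25) patients. The second needs a text amendment and the same count, and gives up the cross-category endpoint. Either way, start logging offers and refusals of testing now, since they may not be recoverable later.
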